shock process. Administration of aldosterone in mice resulted in improved response to phenylephrine⁶. Based on the RCTs performed in human subjects, however, it is controversial whether addition of fludrocortisone provides any true benefit in refractory septic shock patients. Moreover, to date there has not been a trial, whether retrospective or prospective, that has directly compared the use of hydrocortisone alone versus the combination of hydrocortisone and fludrocortisone. Because of this lack of data, we will be investigating the use of hydrocortisone alone versus the combination in critically ill septic shock patients admitted to the medical intensive care unit. Currently, both are considered standard of care both within and outside of the University of Tennessee Medical Center Knoxville.

Objective: To determine if the use of hydrocortisone plus fludrocortisone is associated with a faster resolution of shock (defined as 24 hours vasopressor free) when compared to the use of hydrocortisone alone in medical, critically ill septic shock patients

Study Design and Methods:

This study is a single-center, prospective, open-label, randomized trial which will evaluate adult patients admitted with septic shock to the medical critical care unit (MCC).

Inclusion Criteria:

- Age \geq 18
- Critically ill medicine patients requiring addition of stress dose steroid therapy (hydrocortisone) in addition to pressors for septic shock management during their ICU stay
- Fludrocortisone administered within 24 hours after initiation of hydrocortisone if in combination therapy group

Exclusion Criteria:

- Use of fludrocortisone and/or hydrocortisone for any reason other than septic shock management during ICU stay
- Fludrocortisone/hydrocortisone initiated by any service other than critical care medicine
- Prior use of fludrocortisone/hydrocortisone at time of admission (home or outside facility)
- Patients not appropriate for study inclusion as determined by provider discretion
- Patients receiving steroid therapy not in accordance with assigned group per location (MCC1 or MCC2)
- Patients re-admitted to the MCC during the same admission and restarted on vasopressor therapy will be noted during data collection and only the initial admission will be included for analysis
- Any patient receiving greater than one dose of hydrocortisone 100 mg
- Physical or medical contraindication to receiving PO or PER FT (per feeding tube) fludrocortisone.

Protocol:

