All patients admitted to the medical critical care unit side 1 (MCC1) or side 2 (MCC2) will be provided a “Notice of Research.” At any time, refusal or withdrawal from the study can be requested by the patient, patient advocate, or provider.

Patients that meet inclusion criteria for the study will receive either hydrocortisone 50 mg IV Q6h alone or a combination of hydrocortisone 50 mg IV Q6h plus fludrocortisone 50 mcg PO/PER FT daily. Fludrocortisone must be initiated and administered within 24 hours after the first administered dose of hydrocortisone. Because fludrocortisone is only available as a 100 mcg tablet, the nurse at the bedside will split the tablet into two as to provide a 50 mcg dose. This is standard of practice currently when fludrocortisone is utilized in our institution.

Steroid therapy assignments will be randomized based on patient location. For three consecutive months starting in October 2018, all patients in MCC1 will receive hydrocortisone alone and all patients admitted to MCC2 will receive hydrocortisone plus fludrocortisone. Then, in the following three consecutive months, this will be flipped and MCC1 will receive hydrocortisone plus fludrocortisone while MCC2 will receive hydrocortisone alone. This change in group assignments will occur to account for the difference in number of beds between MCC1 and MCC2, and to minimize the potential differences in patient acuity by location.

Initiation of hydrocortisone for inclusion in the study will be determined solely by provider discretion as the standard of care for septic shock patients. Once hydrocortisone is initiated, fludrocortisone will be initiated within 24 hours for patients on the qualifying side of the unit, unless any of the previously stated exclusion criteria are present. Because these interventions are currently utilized and considered standard of care in the MCC, data collection will be performed retrospectively by generating a list of patients in the MCC receiving hydrocortisone therapy.

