 - Reinitiation of vasopressor therapy (after vasopressor free for 24 hours)
 - Reinitiation of hydrocortisone and/or fludrocortisone
 - Mechanical ventilator free days during ICU admission
 - Duration of steroid therapy
- Safety Endpoints
 - Documentation of two consecutive point of care blood glucose checks >180 mg/dl after initiation of hydrocortisone and/or hydrocortisone/fludrocortisone
 - Gastrointestinal bleed during study period (as documented by provider)
 - Severity of bleed as determined by GUSTO criteria
 - Severe: deadly bleeding; intracerebral bleeding or substantial hemodynamic compromise
 - Moderate: bleeding requiring transfusion
 - Mild: other bleeding not requiring transfusion or causing hemodynamic compromise
 - New initiation of renal replacement therapy during study period
 - Electrolyte abnormalities
 - Sodium level greater than 150 mEq/L during study period
 - Potassium level greater than 5.5 mEq/L during study period

Other Data Collected:

- Demographics: Age, sex, weight, height, BMI, ethnicity (race)
- Septic Shock Bundle initiated
- WBC at time of steroid initiation and at discontinuation

- Initial lactic acid level on admission
- Lactic acid level at initiation of vasopressors
- Vasopressor initiated (norepinephrine, epinephrine, phenylephrine, vasopressin, dopamine, dobutamine)
- Vasopressor dose when steroid therapy was initiated (mcg/min and mcg/kg/min)
- Max vasopressor dose during study period
- SOFA Score
- APACHE Score
- Charlson Comorbidity Index
- Site of infection (lung, intraabdominal, urogenital, skin, CNS, endocarditis, bacteremia, unknown, etc.)
- Non-contaminant, positive culture during study period with clinical correlation to septic shock event
 - Site of culture
 - Gram Positive
 - Gram Negative
 - Viral
 - Fungal
 - Organism
- Comorbidities:
 - Documented heart failure
 - Documented chronic kidney disease stage III-IV not requiring renal replacement therapy at baseline
- Documentation of concurrent cardiogenic shock during study period
- Serum creatinine at initiation of steroid therapy
- Serum creatinine at discontinuation of steroid therapy
- Renal replacement therapy at the initiation of steroid therapy
- Mechanical ventilation at initiation of steroid therapy
- Other systemic steroid use (methylprednisolone, dexamethasone, prednisone) prior to pressor initiation
- Systemic steroid use prior to admission (home medication)

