Frequency and percentage statistics will be used to analyze categorical demographic, predictor, confounding, and outcome variables of interest for the sample. Descriptive statistics will be used to describe the sample characteristics associated with continuous variables. The assumption of normality of continuous distributions will be assessed using skewness and kurtosis statistics. If either statistic is above an absolute value of 2.0, then the distribution will be assumed to be non-normal. Homogeneity of variance between independent groups will be tested using Levene's Test for Equality of Variances. When both statistical assumptions are met, independent samples t-tests will be used to compare the treatment groups on continuous outcomes. Means and standard deviations will be reported and interpreted for these analyses. Mann-Whitney U tests will be used for comparisons when statistical assumptions are violated. Medians and interquartile ranges will be presented and analyzed for non-parametric comparisons. Chi-square tests will be used to test for significant associations between the treatment groups and categorical outcomes. Relative risk with 95% confidence intervals will be reported for significant categorical associations. Multiple regression analysis will be performed with time to resolution of shock as the outcome. Linearity, normality, homoscedasticity, multicollinearity, and autocorrelation assumptions for the regression analysis will be performed. Unstandardized beta coefficients, standard errors of the coefficients, and standardized beta coefficients will be reported and interpreted, along with the change in shared variance (R^2) and respective F-tests. All analyses will be conducted using SPSS Version 22 (Armonk, NY: IBM Corporation) and statistical significance will be assumed at an alpha value of 0.05.

A priori subanalysis will be performed on the following subset of patients: documented history of heart failure and documented chronic kidney disease stage III and IV requiring renal replacement therapy at baseline.

Critical Analysis/Limitations:

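### The steroid-restart endpoint counts a restart of either drug, but only the combination arm is assigned fludrocortisone, so that arm has an extra route to an event

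*Combined protocol and SAP*

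**What the plan says.** The Protocol section sets the two regimens: eligible patients "will receive either hydrocortisone 50 mg IV Q6h alone or a combination of hydrocortisone 50 mg IV Q6h plus fludrocortisone 50 mcg", the fludrocortisone being given once a day by mouth or feeding tube. The Exclusion Criteria list "Patients receiving steroid therapy not in accordance with assigned group per location (MCC1 or MCC2".

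The Outcomes section lists "Reinitiation of hydrocortisone and/or fludrocortisone" as a single secondary endpoint, with no split by drug and no definition of a restart. The line above it does carry a condition: "Reinitiation of vasopressor therapy (after vasopressor free for 24 hours". Two lines further down comes "Duration of steroid therapy", also without a definition.

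For the analysis, the Statistical methods section says: "Chi-square tests will be used to test for significant associations between the treatment groups and categorical outcomes". Relative risks with confidence intervals follow only where an association is significant.

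**The concern.** An outcome compared between arms should be reachable by the same routes in both. Here a control patient can score only by restarting hydrocortisone, while a combination patient can score by restarting hydrocortisone, fludrocortisone or both. A control patient who is given fludrocortisone is, on the exclusion quoted above, removed rather than counted.

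The extra route can only add events to the combination arm, so the direction of any distortion is known even though its size is not. If the difference reached significance, the plan would report a relative risk above 1 for the combination. A reader could take that as a treatment effect when part or all of it came from the definition.

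**Working it through.** **Inputs from the documents.** The regimens (Protocol), the exclusion of off-assignment patients (Exclusion Criteria), the endpoint wording (Outcomes), the chi-square test (Statistical methods), and two-sided alpha 0.05 with 39 per group (Statistical Power).

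**The plan's own figure.** The plan gives no number for steroid restart. The only related figure is the 39 per group for the primary endpoint, used here as the arm size. It can be recovered. With d = 24/36 = 0.667, two-sided 0.05 and an assumed 80% power (the plan states no value), the t-test needs 36.31 per arm. Dividing by the Mann-Whitney efficiency 3/π = 0.955 gives 38.02, which rounds up to 39.

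**Routes to an event.**

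| Restart | Hydrocortisone alone | Combination |
|---|---|---|
| Hydrocortisone only | counts | counts |
| Both drugs | not possible on assignment | counts once |
| Fludrocortisone only | not possible on assignment | counts |

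A joint restart counts once and includes hydrocortisone, so it creates no imbalance if hydrocortisone restarts are equally common. Only the last row does.

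**Assumed rates.** Let *h* be the hydrocortisone restart rate, equal in both arms. Let *f* be the probability of a fludrocortisone-only restart among combination patients who do not restart hydrocortisone. Then:

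- control rate = *h*
- combination rate = *h* + (1 − *h*)*f*
- relative risk = 1 + *f*(1 − *h*)/*h*
- extra events in 39 patients = 39(1 − *h*)*f*

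For example, *h* = 0.10 and *f* = 0.05 give 0.10 + 0.90 × 0.05 = 0.145, a relative risk of 0.145/0.10 = 1.45, and 39 × 0.045 = 1.76 extra events. The last column is the probability that an uncorrected chi-square test at two-sided 0.05 rejects, by exact enumeration with 39 per arm.

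| *h* | *f* | Combination rate | Relative risk | Extra events | Rejection |
|---|---|---|---|---|---|
| 10% | 0% | 10.0% | 1.00 | 0 | 5.9% |
| 10% | 2% | 11.8% | 1.18 | 0.70 | 6.6% |
| 10% | 5% | 14.5% | 1.45 | 1.76 | 10.0% |
| 10% | 10% | 19.0% | 1.90 | 3.51 | 20.9% |
| 20% | 2% | 21.6% | 1.08 | 0.62 | 5.4% |
| 20% | 5% | 24.0% | 1.20 | 1.56 | 7.2% |
| 20% | 10% | 28.0% | 1.40 | 3.12 | 13.4% |
| 30% | 2% | 31.4% | 1.05 | 0.55 | 5.5% |
| 30% | 10% | 37.0% | 1.23 | 2.73 | 10.2% |

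**With hydrocortisone restart as the endpoint.** Both arms have rate *h*, the relative risk is 1.00, and rejection is 5.1% to 5.9% for *h* from 10% to 30%.

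**Duration.** The documents use the term in two ways. The Inclusion Criteria speak of patients "requiring addition of stress dose steroid therapy (hydrocortisone) in addition to pressors", where it means hydrocortisone. The Protocol section says "Steroid therapy assignments will be randomized based on patient location", where it means the whole regimen. On the first use, duration is measured identically in both arms. On the second, it could run to whichever drug stops later. Nothing in the plan chooses between them.

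**The case against.** The strongest reply is that the wording is shorthand for restarting whichever regimen was assigned. The glucose safety endpoint in the same section names the treatments in a similar and/or form, apparently with that meaning. The reading is possible, though not stated. It does not remove the extra route: the combination regimen still contains a second drug, and requiring both to restart would contradict the *or*.

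Second, the exclusion of off-assignment patients might also remove a combination patient who is on hydrocortisone without fludrocortisone, and contraindication to enteral fludrocortisone is itself an exclusion. The plan does not say how either applies to lapses after enrolment. They may make fludrocortisone-only restarts rarer; they do not rule them out.

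Third, every rate above is assumed. That stands. At *f* = 0 there is no bias, and at 2% the excess is well under one event per arm.

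A reader might go further and infer that a single missed and resumed fludrocortisone dose would score, because the vasopressor item has a 24-hour condition and this one has none. The documents do not support that. The missing condition shows that a restart is undefined, not that a brief interruption counts, and resuming a continuing order is not the ordinary sense of a restart. Nor does the plan say that a restart will be interpreted as relapse.

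**Conclusion.** The point holds for the restart endpoint. As written, a fludrocortisone-only restart can count in one arm only, and any that occur raise that arm's rate. How far depends on how often they occur, which the documents do not say. At *h* = 10% the relative risk with no true difference runs from 1.00 (*f* = 0%) to 1.90 (*f* = 10%); at higher *h* it is nearer 1. The figures assume equal hydrocortisone restart rates and 39 per arm.

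Two stronger conclusions are not supported. One is that the combination arm must be expected to show more restarts: that follows only if fludrocortisone-only restarts happen. The other is that steroid duration is asymmetric in the same way: it would be if it ran to the last dose of either drug, but the plan does not say so. What is established there is a missing definition.

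Only secondary endpoints are involved. The primary endpoint and the sample size are untouched.

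**What to change.** Change the between-arm endpoint to *Reinitiation of hydrocortisone*, the drug common to both arms. Report fludrocortisone restarts descriptively, in the combination arm only. In the same edit, state the duration endpoint as *Duration of hydrocortisone therapy*, which keeps the arms comparable whichever meaning was intended.

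The cost is two lines of endpoint wording. No treatment, sample size or primary analysis changes. The small downside is that fludrocortisone restarts are described rather than tested. The plan does not say that dose times for each drug will be abstracted, but checking that fludrocortisone began within 24 hours of hydrocortisone already needs the first-dose time of both. A minimum drug-free interval before a restart counts is not needed for this correction and is left to the investigators.

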While each included patient’s data will be recorded retrospectively after randomization, we do believe that it is necessary to perform this study in a prospective manner rather than fully retrospective. It is not feasible to perform this study retrospectively as we would not be able to ensure adequate and equal numbers in each group within the medical critical care unit, especially considering how medical critical care patients are placed in other intensive care units within our institution based on bed availability. Unequal groups would unduly bias the results and make the analysis less meaningful in terms of contributing to the current body of evidence.

Any medication events, including adverse drug reactions or medication errors, will be routinely reported throughout the study to the UTMC Safety Intelligence system. Routine reports of events related to the study will be reviewed weekly by our medication safety office if necessary. Data will be collected continuously throughout the study duration and investigators will review the data for any concerning safety or efficacy differences between the treatment groups. Upon regular screening for adverse drug events, if any are detected, they will be not only be reported to the Safety Intelligence system but will also be reported for review by the IRB.

Per the FDA guidance for clinical investigators regarding the need for an investigational new drug (IND) application in human research studies, investigations are exempt if the drug is lawfully marketed in the U.S., the investigation is not intended to support a new indication or change the labeling of the drug, the investigation will not support a change in advertising for the drug, and the route of administration, dose, or any other factor of the investigation will not increase the risk associated with the drug⁷. Our study, since we are not changing standard of care and are using accepted, studied doses of hydrocortisone and fludrocortisone, meet these criteria for exemption from IND application.

Outcomes:

- Primary Endpoint:
 - Time to resolution of shock (defined as 24 hours vasopressor free)
- Secondary Endpoints:
 - ICU Length of Stay (LOS)
 - Hospital LOS
 - All-cause mortality at ICU discharge
 - All-cause mortality at hospital discharge
 - All-cause mortality at 28 days of admission
 - All-cause mortality at 90 days of admission
 - Withdrawal of treatment therapy during ICU stay

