Limitations of this study will include the open-label design without blinding and placebo controls. Also, as data collection will be retrospective in nature, we will be relying on nursing documentation for timing of vasopressor initiation and discontinuation for our primary outcome. This could introduce documentation bias, but it is important to point out that our critical care nursing staff document pressor requirements hourly. Also, to note, previous trials have utilized fludrocortisone 50 mcg doses. Currently, the only commercially available fludrocortisone product in the United States is a 100 mcg tablet. In order to comply with the

previously studied dose and the current guideline recommended therapy, we will be utilizing fludrocortisone 50 mcg in our study. This will be achieved by splitting the available 100 mcg tablet in half. Education will be provided to all providers, pharmacists, and nursing involved in the project about the correct dose for fludrocortisone and the appropriate way to order the dose.

Protected Health Information:

Patients and their specific health information will be de-identified to protect privacy. Any information collected that contains PHI will be stored in a secure, locked area on password-protected electronic files that are only accessible to study investigators. Any information containing PHI will be properly disposed of at the end of the study period.

Study Budget: Cost of printing of notification of research

Timeline:

Estimated October 2018 through July 2019

References:

1. Long B and Koyfman A. Controversies in corticosteroid use for sepsis. *J Emerg Med.* 2017; 53 (5): 653-661.

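### Ventilator-free days are counted only within the ICU stay, with no value for death, so the score can favour longer ICU stays or later ICU deaths

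*Combined protocol and SAP*

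**What the plan says.** The Outcomes section lists "Mechanical ventilator free days during ICU admission" among eleven secondary endpoints. The words fix the counting window as the ICU stay. No section gives a start day, a horizon common to all patients, a value for patients who die, or a rule for ventilation that is resumed.

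Death is covered only by separate endpoints: all-cause mortality at ICU discharge, at hospital discharge, and at 28 and 90 days from admission. ICU length of stay is also a secondary endpoint.

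Under Statistical methods, continuous outcomes go to a t-test if skewness and kurtosis are each no larger than 2.0 in absolute value and Levene's test is passed; otherwise they go to Mann-Whitney. Neither route says how deaths are ranked or valued.

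Three other places bear on the point. Other Data Collected includes "Mechanical ventilation at initiation of steroid therapy", so the plan allows for patients who are not ventilated at entry. The Protocol section says that "data collection will be performed retrospectively by generating a list of patients in the MCC receiving hydrocortisone therapy". The Exclusion Criteria limit the analysis to the first stay for patients who return to the unit in the same hospital admission and restart vasopressors.

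**The concern.** A ventilator-free-day score is meant to be higher for patients who come off the ventilator sooner and survive. That needs the same number of countable days for every patient and a worst value for death. Here the number of countable days is the patient's own ICU stay, which is itself an outcome, and death only ends the count.

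A regimen that gets patients out of the ICU sooner could therefore look worse on this endpoint, and one with longer stays or later ICU deaths could look better. The result could also run opposite to ICU length of stay in the same table. The endpoint would be tested and reported on its own, so a reader could take a difference in the wrong direction as benefit or harm.

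**Working it through.** **Inputs.** The window and the absence of a death rule come from Outcomes, and the tests from Statistical methods. The plan gives no numerical assumption for ventilator-free days, so there is no planned figure to reproduce; its 39 per group is for time to resolution of shock. All patient courses below are assumed, with ICU admission and first hydrocortisone dose both on day 0.

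**Step 1: formulas.**
- As written, on the natural reading: score = ICU days − ventilated days.
- Comparison scale: score = 28 − ventilated days if alive at day 28; 0 if dead by day 28.

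**Step 2: individual cases.**

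| Course | As written | 28-day scale, death = 0 |
|---|---|---|
| Extubated day 5, left ICU alive day 6 | 6 − 5 = 1 | 28 − 5 = 23 |
| Extubated day 5, died in ICU day 12 | 12 − 5 = 7 | 0 |
| Extubated day 3, left ICU alive day 4 | 4 − 3 = 1 | 28 − 3 = 25 |
| Extubated day 10, left ICU alive day 11 | 11 − 10 = 1 | 28 − 10 = 18 |
| Never ventilated, left ICU alive day 3 | 3 − 0 = 3 | 28 |
| Never ventilated, left ICU alive day 10 | 10 − 0 = 10 | 28 |
| Never ventilated, died in ICU day 10 | 10 − 0 = 10 | 0 |

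Rows 1 and 2: the death outranks the recovery. Rows 3 and 4: seven more days of ventilation make no difference, because early discharge caps the score. Rows 5 to 7: without ventilation the score is ICU length of stay, and a death on day 10 ties with a survivor discharged that day.

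**Step 3: can whole arms reverse?** Take two hypothetical arms, all patients ventilated from ICU admission. Ventilation and post-extubation ICU times are exponential, and death is independent of both. Arm X has mean ventilation 4 days, mean post-extubation ICU stay 2.5 days and 25% deaths; arm Y has 6 days, 4 days and 35%.
- As written, the mean score is the mean post-extubation ICU stay: 2.5 in X, 4.0 in Y.
- On the 28-day scale, with ventilation mean m and death proportion p, the mean is (1 − p) × [28 − m(1 − e^(−28/m))]. X: 0.75 × 24.00 = 18.0. Y: 0.65 × 22.06 = 14.3.

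X is better on all three inputs, yet scores lower as written and higher on the 28-day scale. This shows that reversal is possible, not that it is likely.

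**Step 4: does the planned choice of test suit the repaired score?** Assume 35% deaths and exponential ventilation with mean 5 days. Then 35% of patients sit at 0 through death, 0.65 × e^(−14/5) = 4% are survivors scoring 14 or less, and 0.65 × (1 − e^(−14/5)) = 61% score above 14. The distribution has two peaks. In simulated samples of 39 with 30% to 40% deaths, under 4% exceeded the 2.0 limit on skewness or kurtosis. The screen would rarely divert this score from the t-test.

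**The case against.** **The formula is the reader's.** The plan states none, so the scores in the table are an interpretation. That stands. But the window is in the text, and ICU days minus ventilated days is its natural reading. If a death value or a longer horizon is intended, it is not written anywhere.

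**The endpoint is minor and has company.** It is one of eleven secondary endpoints, with four mortality endpoints and two lengths of stay reported beside it. That stands and limits misreading, but does not correct the score's direction.

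**Stronger readings to avoid.**
- A reader might infer that length of ventilation drops out of the score altogether. It cancels only when ICU time after extubation is held fixed. With total ICU stay held fixed, each ventilated day still costs one point.
- A reader might infer that the primary endpoint likewise has no start point and loses power. Critical Analysis/Limitations says "we will be relying on nursing documentation for timing of vasopressor initiation and discontinuation for our primary outcome", which implies vasopressor initiation without defining it. Any power loss would depend on the spread of the vasopressor-to-steroid delay and on whether the planned 36-hour SD already includes it; the documents give neither. Moving that clock to the first steroid dose would be a trade-off, since "Initiation of hydrocortisone for inclusion in the study will be determined solely by provider discretion" in an open-label trial. Stating the start is a wording note, as is saying which admission the 28- and 90-day mortality endpoints run from.

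**A 28-day score brings its own problems.** Its day 28 differs from that of the mortality endpoint, patients discharged while ventilated need a rule, and scoring death as 0 makes the distribution two-peaked. All three are right and are dealt with in the fix.

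**Conclusion.** The point holds for the ventilator-free-day endpoint. As worded, it can rank a later ICU death above an early recovery (7 against 1, where a 28-day scale gives 0 against 23), and it rewards a longer ICU stay in patients who are never ventilated. This rests on reading the score as ICU days minus ventilated days and on illustrative courses. The documents give no ventilation times or death rates, so neither the frequency of reversals nor the likely bias between arms can be estimated. The primary analysis and the sample size of 78 do not depend on it. It is an inexpensive improvement to one secondary endpoint, worth making before data are abstracted.

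**What to change.** Replace the endpoint with days alive and free of mechanical ventilation from the first hydrocortisone dose to day 28, and state that:
- death by that day 28 scores 0;
- any re-ventilated day counts as ventilated;
- patients discharged from hospital alive and off the ventilator are assumed unventilated afterwards;
- patients discharged while ventilated count as ventilated to day 28;
- this day 28 runs from the first hydrocortisone dose, so it differs from the 28-day mortality endpoint, which runs from admission;
- this endpoint is an exception to the initial-admission rule in the Exclusion Criteria;
- arms are compared by Mann-Whitney for this endpoint whatever the normality screen shows.

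**Cost.** Ventilator and vital status must be looked up in hospital records to day 28 after the patient leaves the unit. Status after hospital discharge is partly assumed. The start of the count is a clinician-chosen event in an open-label trial, to be noted as a limitation. The study calendar should not suffer: if the last first dose is on 31 March 2019 (assumed end of the two three-month periods), day 28 is 28 April 2019, 64 days before 1 July in the month the plan gives as its end.

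### The sodium and potassium safety endpoints have no baseline value and no new-onset condition, so abnormalities already present at steroid start count as events and dilute the comparison

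*Combined protocol and SAP*

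**What the plan says.** Under Outcomes, Safety Endpoints, the two electrolyte endpoints are "Sodium level greater than 150 mEq/L during study period" and "Potassium level greater than 5.5 mEq/L during study period". No section defines when the study period starts or ends.

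Two endpoints in the same list are limited. Glucose is tied to steroid start: "Documentation of two consecutive point of care blood glucose checks >180 mg/dl after initiation of hydrocortisone and/or hydrocortisone/fludrocortisone". Renal replacement must be new: "New initiation of renal replacement therapy during study period". The gastrointestinal bleed endpoint, like the electrolytes, is tied only to the study period.

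Other Data Collected includes "Serum creatinine at initiation of steroid therapy" and "Renal replacement therapy at the initiation of steroid therapy", and also white cell count and ventilation status at that time. It lists no sodium or potassium at any time. SOFA and APACHE are listed as scores, without their component values.

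For the analysis, Statistical methods says "Chi-square tests will be used to test for significant associations between the treatment groups and categorical outcomes". Regression is planned only for the primary outcome, and relative risks are to be reported only for significant associations.

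**The concern.** Patients in septic shock may already have an abnormal sodium or potassium when hydrocortisone is started. As defined, the endpoints cannot separate such a patient from one whose value first crosses the threshold on treatment. Cases present at the start say nothing about the effect of adding fludrocortisone. They raise the event rate in both arms and so pull the comparison toward no difference.

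This matters most for sodium. Background and Rationale gives increased sodium reabsorption as the action of the added drug, so a high sodium is the listed safety measure tied most directly to the combination. For potassium the documents give no such link, and the point there rests only on the same missing baseline.

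**Working it through.** **The plan's own figure.** The documents give no expected rate, effect or power for the electrolyte endpoints. The only relevant figure is the 39 per group set for the primary endpoint. With d = 24/36 = 0.667, two-sided alpha 0.05 and 80% power (assumed, since none is stated), a two-sample t-test needs 36.3 per group. Dividing by the Mann-Whitney efficiency 3/π = 0.955 gives 38.02, rounded up to 39. The figure reproduces. It serves below only as the size of the safety comparison.

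**Does the meaning of the study period matter?**
- If it opens at ICU admission, every value above the threshold before steroids counts, including values that had returned to normal by the first dose.
- If it opens at the first hydrocortisone dose, values that had already returned to normal drop out, but a value still above the threshold counts.

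Under both readings, an abnormality present at steroid start is an event.

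**Dilution.** Let b be the share of patients already above the threshold, equal in both arms, and q the risk of a new abnormality among the rest.

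Observed risk = b + (1 − b)q

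Observed risk difference = (1 − b)(q₂ − q₁)

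Observed relative risk = [b + (1 − b)q₂] / [b + (1 − b)q₁], which is nearer 1 than q₂/q₁ for any b above 0 when q₁ and q₂ differ.

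Assume q₂ = 20% (combination) and q₁ = 10% (hydrocortisone alone). At b = 10%, for example, the risks are 0.10 + 0.90 × 0.20 = 0.28 and 0.10 + 0.90 × 0.10 = 0.19, and 0.28/0.19 = 1.47. Power is for two proportions at two-sided alpha 0.05, with 39 per arm as written and 39(1 − b) per arm if only new abnormalities are counted among patients normal at baseline.

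| b | Combination | Alone | Risk difference | Relative risk | Power as written | Power, new only |
|---|---|---|---|---|---|---|
| 0% | 20.0% | 10.0% | 10 points | 2.00 | 23% | 23% |
| 5% | 24.0% | 14.5% | 9.5 points | 1.66 | 18% | 22% |
| 10% | 28.0% | 19.0% | 9 points | 1.47 | 15% | 21% |
| 20% | 36.0% | 28.0% | 8 points | 1.29 | 11% | 19% |

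With a larger assumed effect, 30% versus 10%, and b = 20%, the risks are 44% and 28%. The relative risk is 1.57 instead of 3.00, the risk difference 16 points instead of 20, and power 31% as written against 51% counting new abnormalities only.

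**Imbalance.** Pure dilution needs equal b in the two arms. Even with independent allocation of 39 per arm, the standard deviation of the chance difference in b is √[2b(1 − b)/39], or 6.8 points at b = 10% and 9.1 points at b = 20%. With the same q values, suppose b is 10% in the combination arm and 20% in the other. The observed risks are then 0.10 + 0.90 × 0.20 = 0.28 and 0.20 + 0.80 × 0.10 = 0.28, so a true doubling shows as a relative risk of 1.00. With the imbalance reversed, they are 0.20 + 0.80 × 0.20 = 0.36 and 0.10 + 0.90 × 0.10 = 0.19, a relative risk of 1.89. The listed data would not reveal either situation, and an unadjusted chi-square test would not correct for it.

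**The case against.** The strongest objection is that sample size, not the definition, dominates. Even with no baseline cases, 8/39 against 4/39 gives a relative risk of 2.0 with a 95% interval of about 0.66 to 6.1, which contains every diluted value in the table. At 20% versus 10% and b = 20%, the fix raises power only from 11% to 19%. A reader might infer that the definition makes a falsely reassuring result on sodium likely. The documents do not support that: every rate here is assumed, and a true doubling would usually be missed even with perfect baseline data. This part of the objection stands. The gain is larger for larger effects, but those are assumed too. On the absolute scale the loss is also modest, from 10 points to between 8 and 9.5.

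Three other points stand:
- A reader might infer that each abnormal value is attributed to treatment. The plan only compares frequencies between arms.
- The electrolytes are not the only unanchored safety endpoints, since gastrointestinal bleeding is worded the same way.
- Exchanging the regimens between the two unit sides after three months partly limits differences by location. It does not remove chance or calendar imbalance.

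A reader might also infer that the baseline information is lost. It is not: "data collection will be performed retrospectively by generating a list of patients in the MCC receiving hydrocortisone therapy", so the values can be taken from the chart. They are only absent from the list. That makes the gap easier to repair, but does not excuse it.

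**Conclusion.** The point holds as a definitional weakness in two safety endpoints. It does not touch the primary analysis. Followed as written, the plan counts abnormalities already present at steroid start as events, under either reading of the study period, and nothing in the listed data or planned analysis separates them afterward.

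The direction of the dilution follows from algebra, given equal baseline prevalence in the arms and some difference in new-onset risk. Its size cannot be derived from the documents, and the relative risks of 1.66, 1.47 and 1.29 in place of 2.0 are illustrations only. If baseline prevalence differs between arms, the bias can go either way. With about 39 patients per arm these comparisons remain imprecise after any correction, so this is an inexpensive improvement and not a defect that decides what the trial can conclude.

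**What to change.** 1. Define the study period for the two electrolyte endpoints as starting at the first hydrocortisone dose, which is common to both arms, and state when it ends.
2. Add to Other Data Collected the last sodium and the last potassium at or before that dose.
3. Define each endpoint as a first value above the threshold after that dose, among patients at or below the threshold at baseline.
4. Tabulate by arm the patients above the threshold at baseline, including any further rise, so that worsening is not lost.

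The cost is two more routine chart values per patient, a change of wording, and a slightly smaller denominator for each endpoint: 39 × 0.90, or about 35 per arm, if 10% are abnormal at baseline. The fix does not make these endpoints well powered, and the report should not read a non-significant difference as evidence of safety.
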